13.2 Study Endpoints and Analysis Plan

All subjects who receive at least one dose of study drug will be considered evaluable and included in the efficacy and safety analysis.

Analytic plan for primary objective:

The primary efficacy null hypothesis of the equality of time to improvement (2 points) in clinical status curves will be tested with the log-rank test. The overall type I error for the primary analysis will be considered one-sided alpha of 0.025. Kaplan-Meier estimates will be reported for each of the two arms with median time to improvement and 95% confidence intervals (CI). Cox regression will be employed to estimate the treatment effect (HR) and 95% CI.

Analytic plan for secondary and exploratory objective:

We will estimate the distributions of all time-to-event endpoints using the Kaplan-Meier method and if possible, provide medians (95% CI). Comparisons between survival curves will be assessed using log-rank tests and Cox regression models.

For each arm, we will estimate the 1-month mortality rate and incidence of adverse events graded by CTCAE v5.0 using the exact 95% confidence intervals. Comparisons between the two arms will be assessed using chi-squared or Fisher's exact tests. The mean/medians of the 7-point ordinal scores at day 14 after the start of treatment will be computed and compared between the two groups using two-sample t-test or the equivalent non-parametric Wilcoxon Rank-Sum test if normality is not satisfied.

Changes in exploratory endpoints (before and after treatment) will be quantified using means (95% CI) and/or medians (inter-quartile ranges) for non-normal data. Comparisons between the two arms will be made using two-sample independent t-tests or the non-parametric equivalent, Wilcoxon Rank-Sum test. The associations between baseline levels and/or changes over time of IL-8 and other key cytokines (TNF, IL-1b, IL-6) with outcomes will be assessed using regression models.

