5.1 Inclusion Criteria

- Male or female adult ≥ 18 years of age at time of enrollment.
- Confirmed diagnosis of SARS-CoV-2 infection ≤ 14 days prior to registration.

- Inpatient hospitalization (or documentation of a plan to admit to the hospital if the patient is in the emergency department)
- Evidence of pneumonia by chest radiographs, chest CT **OR** chest auscultation (rales, crackles).
- Severe respiratory disease (oxygen saturation $\leq 93\%$ on room air or requires $\geq 2\text{L}$ oxygen by NC in order to maintain $\text{SaO}_2 \geq 93\%$) **OR** critical respiratory disease (requiring non-rebreather, non-mechanical/mechanical ventilation, high-flow nasal cannula, ICU admission).
- Patients can continue their anti-cancer therapy at the discretion of the treating physician.
- *Adequate laboratory tests including:*
 - ANC $>500 \text{ cells/mm}^3$
 - Platelet count $>20,000 \text{ cells/mm}^3$
 - Serum total bilirubin $<1.5 \times \text{ULN}$
 - ALT $<5 \times \text{ULN}$
 - AST $<5 \times \text{ULN}$
- *Age and Reproductive Status*
 - a) Males and females, aged at least 18 years old
 - b) Women of childbearing potential (WOCBP) must have a negative serum or urine pregnancy test (minimum sensitivity 25 IU/L or equivalent units of human chorionic gonadotropin) within 24 hours prior to the start of study treatment.
 - c) Women must not be breastfeeding.
 - d) WOCBP must agree to follow instructions for method(s) of contraception for the duration of study treatment plus for a total of 155 days post treatment completion. Local laws and regulations may require use of alternative and/or additional contraception methods.
 - e) WOCBP who are continuously not heterosexually active are also exempt from contraceptive requirements, but should still undergo pregnancy testing as described in this section.
 - f) Males who are sexually active with WOCBP must agree to follow instructions for method(s) of contraception during study treatment with BMS-986253 for a total of 215 days post-treatment completion.
 - g) Azoospermic males are exempt from contraceptive requirements. WOCBP who are continuously not heterosexually active are also exempt from contraceptive requirements, and still must undergo pregnancy testing as described in this section.
- Willingness to provide written informed consent and HIPAA authorization for the release of personal health information, and the ability to comply with the study requirements

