7.5 Randomization and Blinding

Patients will be randomized 2:1 (anti-IL8: standard of care) in “real-time”. If the subject’s eligibility status is confirmed, the statistician will send the randomization assignment based on the pre-generated randomization scheme.

This is an open-label study.

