10.1 Screening/Pretreatment Evaluation

Before initiating any screening activities, the scope of the study should be explained to each patient. Patients should be advised of any known risks inherent in the planned procedures, any alternative treatment options, their right to withdraw from the study at any time and for any reason, and their right to privacy. After this explanation, patients should be asked to sign and date an IRB-approved informed consent form that meets the requirements of the Code of Federal Regulations (Federal Register Vol. 46, No. 17, January 27, 1981, part 50).

The pretreatment/screening visit will determine patient eligibility according to the inclusion and exclusion criteria. All subjects must undergo a number of baseline evaluations as part of this screening visit, as detailed below. All of these evaluations should be conducted within 1 day of starting the protocol. This information is also summarized in the Study Calendar (Table 1).

- informed consent
- demographic information
- medical history, including review of systems and baseline ECOG score.
- physical assessment
- vital signs: temperature, pulse, blood pressure, respiratory rate, oxygen saturation and FIO₂ and SpO₂/FIO₂
- height and weight
- current medication list, including drug allergies/adverse events
- hematological laboratories (hemoglobin, hematocrit, white blood cell count with differential [including absolute eosinophil count], platelets)
- coagulation profile (INR, aPTT)
- serum chemistry (sodium, potassium, chloride, bicarbonate, urea, creatinine, glucose, calcium, albumin, protein, bilirubin, ALT, AST, alkaline phosphatase)
- CRP, D-Dimer, LDH, sIL-6 level
- Neutrophil-to-lymphocyte ratio (NLR), absolute lymphocyte count
- NEWS2 score
- 7-point ordinal score
- CT or CXR of the chest (optional)
- Sera for biomarker and PK analysis.

After all relevant screening information is documented, registration should be finalized and appropriate documents (*i.e.*, signed informed consent, supporting source documentation for eligibility) should be faxed or emailed to CPDM Central Registration Office for review.

Information on patients who do not meet eligibility criteria to participate in this study (*i.e.*, screening failures) should also be captured.

10.2 During Hospitalization:

The following must be performed during hospitalization (if screening assessments done <1 day prior to first treatment dose, they do not need to be repeated on Day 1 of treatment).

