13.3 Subgroup Analysis

A post-hoc, subgroup analysis will be employed to compare the primary and secondary endpoints for cancer vs non-cancer patients.

A post-hoc, subgroup analysis based on severity of respiratory symptoms is also planned to investigate the consistency or heterogeneity of the treatment effect across the following pre-specified groups:

- 1) Severe Respiratory Disease – defined as oxygen saturation $\leq 93\%$ on room air, RR ≥ 24 or $\geq 50\%$ lung involvement on imaging within 24 - 48hrs.
- 2) Critical Respiratory Disease – defined as respiratory failure requiring non-rebreather, high-flow nasal cannula, ICU admission, non-invasive ventilation, invasive ventilation.

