13.4 Interim analyses

One interim analysis is planned after approximately 17 (40% of the total 41 events) have been observed using O'Brien and Fleming stopping boundary using the Lan-DeMets spending function at a nominal type I error of 0.025. The intent-to-treat (ITT) principle is applied to the analysis, and therefore, we inflated the sample size by 5% to safeguard against drop-outs.

An independent Data Safety Monitoring Committee (DSMC) will serve as the primary reviewer of the results of the interim analyses of the study and will make recommendations for discontinuation of the study or protocol modifications. Stopping rules for overwhelming efficacy and/or futility are provided in Table 4 below.

Table 4. Efficacy and Boundaries and Properties for the Time to Improvement Analysis

Analysis*	Value	Efficacy	Futility
IA1: 40%	Nominal critical point Z-value	3.3569	0.0811
N: 138	p (1-sided)	0.0004	0.4677
Events: 17	~HR at bound	0.1720	0.9584
Month: 2.6	P(Cross) if HR=1	0.0004	0.5323
	P(Cross) if HR=0.4	0.0599	0.0427
IA2: 100%	Nominal critical point Z-value	1.9622	1.9622
N: 138	p (1-sided)	0.0249	0.0249
Events: 41	~HR at bound	0.5217	0.5217
Month: 7	P(Cross) if HR=1	0.0240	0.9760
	P(Cross) if HR=0.4	0.8000	0.2000

*This column displays the number of events and percentage (%) of needed time to improvement events, the expected sample size (N), and the estimated months (Month) after first participant is randomized for each analysis.

p (1-sided): the nominal α for testing.

~HR at bound: the approximate hazard ratio required to reach the bound for overwhelming efficacy or futility stop.

P (Cross if HR=1): the probability of crossing a bound at or before each analysis under the null hypothesis.

P (Cross if HR=0.40): the probability of crossing a bound at or before each analysis under the alternative hypothesis.

Abbreviations: HR = hazard ratio; IA = interim analysis.

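### The primary log-rank test and Cox model take no account of baseline severity, although the 7-point score is recorded at screening and enrolment reaches mechanical ventilation

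*Combined protocol and SAP*

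**What the plan says.** For the primary endpoint, Section 13.2 plans that the "clinical status curves will be tested with the log-rank test" and that "Cox regression will be employed to estimate the treatment effect (HR) and 95% CI". No stratum or covariate is attached to either. The regression models at the end of 13.2 relate cytokines to outcomes and do not adjust the primary comparison. On error control: "The overall type I error for the primary analysis will be considered one-sided alpha of 0.025".

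On allocation, Section 7.5 gives a 2:1 ratio and says "the statistician will send the randomization assignment based on the pre-generated randomization scheme". It does not say whether that scheme is stratified. The synopsis and Sections 4.1 and 13.1 name no factor either.

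Eligibility in Section 5.1 starts at saturation of 93% or below on room air, or at least 2 L of oxygen by nasal cannula, and extends to "critical respiratory disease (requiring non-rebreather, non-mechanical/mechanical ventilation, high-flow nasal cannula, ICU admission". The "7-point ordinal score" is in the screening list of Section 10.1 and is marked at screening in the study calendar.

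Severity enters the analysis plan only in Section 13.3: "A post-hoc, subgroup analysis based on severity of respiratory symptoms is also planned". On timing, Section 13.4 says: "One interim analysis is planned after approximately 17 (40% of the total 41 events) have been observed".

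**The concern.** The event is a gain of 2 points from the patient's own baseline (Section 11.1.1). That does not make event rates comparable across starting levels, because the step differs in kind. From score 4 it means reaching 6: off oxygen and no longer in need of medical care. From score 2 it means reaching 4: off the ventilator but still on oxygen. Baseline score may therefore be strongly related to time to improvement.

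If it is, two things follow. The unstratified log-rank test loses power, because patients with very different event rates share one risk set. And a chance difference in severity between 92 treated and 46 control patients, with fewer still at the 41-event analysis, feeds straight into the primary result. In an open-label trial, an adjustment chosen after outcomes have been seen would carry little weight.

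**Working it through.** **Plan's own figure.** Inputs: HR 0.40, one-sided alpha 0.025, 80% power, 2:1 allocation, 41 events (Sections 13.1, 13.2 and 13.4). Schoenfeld's formula for an unstratified log-rank test:

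events = (1.960 + 0.842)² / [(2/3)(1/3)(ln 0.40)²] = 7.849 / (0.2222 × 0.8396) = 42.07, or 43 rounded up.

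Power at 41 events = Φ(√(41 × 2/9) × 0.9163 − 1.960) = Φ(0.806) = 0.79.

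The stated 41 events and 80% are thus reproduced closely with no allowance for severity.

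**Assumptions for the comparison.** The documents give no severity mix and no improvement rate by level, so these are assumed:
- 60/25/15% of patients at scores 4/3/2, with 92 vs 46 allocated without regard to score;
- exponential times within each level, and follow-up to day 28;
- an improvement-rate ratio of 2.5 (1/0.40) favouring anti-IL-8, the direction given in the synopsis;
- uniform accrual over 210 days (90 days changes the powers by at most 4 points);
- no deaths or drop-out.

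**Power at 41 events, one-sided critical value 1.96 (8,000 simulated trials per row):**

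| Control medians at scores 4/3/2 (days) | Unstratified | Two levels (4–5 vs 2–3) | Three levels |
|---|---|---|---|
| 4/4/4 (not prognostic) | 71.2% | 67.0% | 64.4% |
| 4/6/9 | 65.9% | 66.6% | 65.1% |
| 4/8/20 | 53.7% | 64.4% | 65.1% |
| 4/12/40 | 41.0% | 64.4% | 66.8% |

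About 43–48 patients (14–16 controls) are in the analysis at that point. Schoenfeld's formula is a small-effect approximation, so the columns should be compared with each other and not with 79%.

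**Variations, unstratified vs two-level:**
- Table 4 bounds at 17 and 41 events, times rounded up to whole days, rows in the same order: 70.5 vs 66.7%; 64.6 vs 66.2%; 53.6 vs 64.3%; 41.4 vs 63.3%.
- Milder mix, 80/15/5%: 73.4 vs 70.8%; 69.4 vs 69.4%; 62.1 vs 69.6%; 51.8 vs 69.3%.
- Reversed gradient 9/6/4, mix 60/25/15%: 69.5 vs 69.4%.
- All 138 patients followed to day 28, ratio 2.5: 99.7 vs 99.7%; 99.5 vs 99.8%; 96.4 vs 99.5%; 87.2 vs 99.2%.

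**Chance imbalance.** With 25 + 15 = 40% at scores 2–3, the standard error of the difference between arms is √(0.4 × 0.6 × (1/92 + 1/46)) = 0.0885. The chance that control is worse by at least 10 percentage points is 1 − Φ(0.10/0.0885) = 1 − Φ(1.13) = 0.13. Simulation gives about 12%, and the opposite imbalance is about as frequent.

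One-sided false-positive rate with no treatment effect, all 138 followed to day 28, in trials where control is at least 10 points worse:

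| Control medians (days) | Unstratified | Two levels |
|---|---|---|
| 4/4/4 | 2.4% | 2.3% |
| 4/6/9 | 4.9% | 1.7% |
| 4/8/20 | 8.0% | 2.8% |

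These rest on the roughly one trial in eight that meets the condition, so they carry simulation error. Repeat runs gave 5.4–5.6% vs 1.9–3.0% for 4/6/9 and 7.7–9.5% vs 2.6–3.2% for 4/8/20. When the imbalance runs the other way, the unstratified rate falls to 0–1.5%, while the stratified rate stays at 2.2–2.4%. Over all trials both tests reject in 2.0–2.5%.

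**The case against.** **The planned test is valid.** This stands. Randomisation protects the unadjusted log-rank test, and the sizing is consistent with it. Stratifying is a matter of efficiency and robustness, not the repair of an error.

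**The gain rests on assumed figures.** This also stands. There is nothing to gain with 4/6/9 medians, with the reversed gradient, or with the milder mix at 4/6/9. The large gains need a five- or ten-fold spread in medians. Because the 2-point step differs by level, even the direction of the gradient cannot be settled from the documents.

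**The randomisation may already be stratified.** It may be; the scheme is not in the documents. The 12% imbalance frequency assumes that it is not balanced on severity. If it is balanced, that part of the concern falls away, but the power argument remains.

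**Table 4 lists N 138 at both looks, and with everyone followed to day 28 the difference nearly vanishes at the design effect.** This is partly right. That result also leaves out patients who never improve. With assumed non-improvers of 10/25/45% at scores 4/3/2, power fell sharply for both tests and stratifying gained 11–16 points.

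**Seventeen interim events are sparse for two strata.** This does little harm. At the design effect, the chance of crossing the interim futility bound is 8.6% stratified vs 7.4% unstratified when score is not prognostic, and 9.7% vs 12.0% with 4/8/20.

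**Conclusion.** The concern holds, as an improvement that should be made and not as a validity error. No stratum, covariate or stratification factor is stated, although the value needed is collected at screening.

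The size is conditional on the assumed mix and medians. At 41 events, two-level stratification costs about 4 points of power if baseline score is not prognostic, changes little under a mild gradient, and gains about 11 points at 4/8/20 and 23 at 4/12/40. Its power stays between 64% and 67% across these cases, while that of the unstratified test runs from 71% down to 41%. When severity is prognostic and imbalanced by chance, the unstratified false-positive rate moves well above or well below 2.5%, depending on which arm is sicker. The stratified rate stays near nominal. Confidence in the size is medium, because deaths and drop-out are not in the main calculations.

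**What to change.** Before any comparison of outcomes by arm:

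- **Section 13.2:** state that the primary log-rank test, at the interim and at the final look, is stratified by baseline 7-point score in two levels (4–5 vs 2–3), and that the primary hazard ratio comes from a Cox model stratified by the same factor. Keep the unadjusted log-rank test and Cox model as sensitivity analyses.
- **Section 7.5:** state whether the randomisation is stratified and, if so, by what.
- **Definition of the stratum:** use the recorded score, not the severe and critical groups of Section 13.3. Those groups count non-rebreather patients as critical, whereas supplemental oxygen is score 4 on the scale.

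Two levels are preferable to three: if score turns out not to be prognostic, two levels lose about 3–4 points of power at 41 events and three lose about 6–7. The cost is one sentence in each section and no new data. The power in Table 4 should be labelled as calculated without strata.

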2. STUDY OBJECTIVES

Primary Objective

- To determine the **time to improvement in the 7-point ordinal scale** in patients treated with anti-IL-8 therapy compared to standard of care/controls.
 - Measured from baseline to 2 point or greater improvement in 7-point ordinal scale.

Secondary Objectives

- To evaluate the **time to death** in patients treated with anti-IL-8 therapy compared to controls.
- To evaluate the **mortality 1 month** after start of treatment in patients treated with anti-IL-8 therapy compared to controls.
- To determine the **time to intubation** in patients treated with anti-IL-8 therapy compared to controls.
 - Measured from time of disease onset to time of intubation.
- To estimate the **time to improvement in oxygenation** in patients treated with anti-IL-8 therapy compared to controls.
 - Measured as time from start of treatment until $\geq 30\%$ decrease in oxygen requirement compared to baseline
- To measure the **proportion of patients requiring ICU admission at 1 month** in patients treated with anti-IL-8 therapy compared to controls.
 - Measured as the number of patients requiring ICU admission over their hospitalization over the number of evaluable patients.
- To assess the **safety and tolerability** defined as adverse events graded by CTCAE v5.0 in patients treated with anti-IL-8 therapy compared to controls.
- To assess the **duration of hospitalization** in patients treated with anti-IL-8 therapy compared to controls.
 - Measured as time from admission to time of discharge.
- To compare the raw 7-point ordinal scale scores at day 14 in patients treated with anti-IL-8 therapy versus controls.

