10. STUDY CALENDAR

Every effort should be made to keep visits, tests, and procedures on schedule. Acceptable deviations are listed below.

	Screening Evaluation ^a	During Hospitalization (daily unless indicated)	Day 29 and Follow-up (after discharge) ^f
Informed consent	X		
Medical history (including baseline ECOG)	X		X
Review of medications	X	X	X
Physical assessment ^k	X	X	
Vital signs (including SpO ₂ /FIO ₂ if on supplemental oxygen)	X	(3 times per day) ⁱ	
Height and weight	X		
Laboratory studies ^b	X	X	
Inflammatory markers ^j	X	Every 2 days	
NLR and absolute lymphocyte count	X	X	
Serum ^c	X	Every 7 days (+/- 2 days) ^c	
NEWS2 score ^d	X	X	
7-point ordinal scale ^l	X	X	
Chest imaging (optional) ^e	X	Every 7 days (+/- 2 days) ^e	
BMS-986253 dose		Every 2 weeks for 1-3 doses ^g	
Toxicity assessment		X	X ^h

a: The screening (pre-treatment) evaluation should be conducted within 1 day prior to dose of BMS-986253. If screening done on same day as treatment then treatment day 1 assessments do not need to be repeat (screening assessments will suffice)
b: Laboratories should include hemoglobin, hematocrit, white blood cell count with differential (including absolute eosinophil count), platelets, sodium, potassium, chloride, bicarbonate, urea nitrogen, creatinine, glucose, calcium, albumin, total protein, bilirubin, alanine aminotransferase (ALT), aspartate aminotransferase (AST), alkaline phosphatase. Prothrombin time (PT/INR), activated partial thromboplastin time (APTT) will be drawn at baseline and then as clinically indicated.
c: Serum samples should be collected for cytokine and PK analysis at screening, day 8, 15, 22, 29, and EOT if possible (not required). Should be collected prior to the treatment dose of day 15 and 29. For patients ready for discharge prior to day 8, a serum sample should be collected, when feasible, prior to discharge.
d: NEWS2 score is calculated considering respiratory rate, oxygen saturation, systolic blood pressure, pulse rate, level of consciousness/confusion, temperature.
e: CT chest or CXR at baseline (within 2 days of enrollment) and after 7 days (+/- 2 days) if clinically indicated.
f: Can be done by phone: at day 29 (+/- 1 day) and every 1 month (+/- 1 week) (until 100 days following last dose of treatment), then every 3 months (+/- 1 month) from registration to up to 1 year follow up.

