11.2 Secondary Endpoints

11.2.1 *Time to death*

The time to death will be defined as the time from onset from symptoms until death from any cause. Patients who are alive or lost to follow-up at the cut-off date will be censored from this analysis.

11.2.2 *Mortality at 1 month*

1-month mortality is defined as the percentage of patients who have died 1 month from the time of start of treatment.

11.2.3 *Time to intubation*

The time to intubation will be defined as the time from symptom onset until time of intubation. Any patients already intubated at enrollment will be censored from this analysis.

11.2.4 *Time to improvement in oxygenation*

The time to improvement in gas exchange will be defined as the time from time of start of treatment until a $\geq 30\%$ decrease in oxygen requirement compared to

baseline [or elimination of oxygen requirement] without a decrease in SpO2 sustained for at least 48hrs or until discharge.

11.2.4 *Proportion of patients requiring ICU admission at 1 month.*

The proportion of patients requiring ICU admission will be calculated as the number of patients requiring ICU admission over the course of their hospitalization over the number of evaluable patients.

11.2.5 *Safety and Toxicity*

All subjects receiving at least one dose of the study drug will be evaluated for safety by monitoring symptoms, physical examinations, and laboratory tests. Adverse events will be classified and graded according to the NCI Common Toxicity Criteria version 5.0 (see Appendix A). The absolute number and frequency of each adverse event will be reported, and subdivided according to toxicity grade. A description of adverse events by treatment arm will also be reported. A particular adverse event occurring more than once in the same subject will be counted only once and at its worse grade.

11.2.6 *Duration of Hospitalization*

Duration of hospital admission will be measured from the time of admission until the time of discharge.

11.2.7 *7-point Ordinal Scale Score*

The mean/medians of the 7-point ordinal raw scores at day 14 from the start of treatment will be computed and compared between the treatment and control groups.

Exploratory Endpoints.

11.2.8 *Change in inflammatory markers from baseline*

Changes in LDH, D-Dimer, CRP, ESR, NLR and absolute lymphocytes before and after treatment and over time will be measured every other day during hospitalization.

11.2.9 *Change in circulating sIL-6 levels from baseline*

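### The day-14 ordinal comparison leaves out the baseline score recorded at screening: a valid test, but an inefficient one if baseline severity is prognostic

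*Combined protocol and SAP*

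**What the plan says.** The day-14 score is a secondary objective: "To compare the raw 7-point ordinal scale scores at day 14 in patients treated with anti-IL-8 therapy versus controls" (section 2). Section 11.2.7 repeats that it is the raw score that is compared: "7-point ordinal raw scores at day 14 from the start of treatment will be computed and compared between the treatment and control groups". Section 13.2 names the test. The scores are "compared between the two groups using two-sample t-test" "or the equivalent non-parametric Wilcoxon Rank-Sum test if normality is not satisfied". No covariate is named here or for any other efficacy model, and no power, effect size or alpha is given for this endpoint.

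The baseline value exists. Section 10.1 lists the "7-point ordinal score" among the screening evaluations, and the study calendar in section 10 shows it at screening and daily in hospital. Section 5.1 admits patients with severe disease (saturation of 93% or less on room air, or at least 2 L by nasal cannula) and also those with "critical respiratory disease (requiring non-rebreather, non-mechanical/mechanical ventilation, high-flow nasal cannula, ICU admission"). On the trial's scale that is roughly levels 2 to 4, possibly 5. Section 7.5 describes a pre-generated 2:1 scheme and mentions no stratification. Section 13.3 plans severe and critical subgroups, but to examine heterogeneity of effect; it does not adjust the overall day-14 comparison.

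**The concern.** A patient who starts on a ventilator and one who starts on 2 L of oxygen are unlikely to have the same day-14 prognosis. If so, much of the spread in day-14 scores is already explained at entry, and a test that ignores entry status treats that spread as noise. What is at stake is power for this secondary comparison.

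With 46 controls and no described stratification, chance imbalance in severity is also plausible, and the planned test makes no allowance for it in the observed data. A lesser matter is that a bounded seven-level score with death at one end and discharge at the other gives no reason to start from a t-test and let an unspecified normality check decide.

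**Working it through.** **The plan's own figure.** There is none for day 14. The only power statement concerns the primary log-rank test: 41 events, 80% power, one-sided 0.025, HR 0.40, 2:1. Schoenfeld's formula gives (1.960 + 0.842)² / [(2/3)(1/3)(ln 0.40)²] = 42.07 events, and 79.0% power at 41 events. The stated figure therefore reproduces, and it does not involve the day-14 score.

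**Inputs from the documents.** 92 versus 46 patients (13.1); a seven-level scale from death to not hospitalised (11.1.1); entry at about levels 2 to 4 (5.1).

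**Assumed inputs, not in the documents.**
- Baseline levels 2/3/4 at 20/30/50%.
- A reference day-14 distribution over scores 1 to 7 of 15/12/6/12/8/5/42%.
- A common odds ratio of 2.0 or 2.5, tested two-sided at 0.05.
- A known day-14 score for every patient. After discharge this would itself have to be assumed, because the first planned call is Day 29.

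**Model.** logit P(Y ≥ k) = α_k + β·arm + γ_baseline, with β = ln(OR) and prognostic strength d = γ_4 − γ_2 varied from 0 to 3. These values of d correspond to baseline/day-14 correlations of about 0.0, 0.2, 0.4 and 0.5. There were 2,000 to 6,000 trials per setting, with simulation error of about 1 point.

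Power (%), 20/30/50% mix:

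| OR | d | t-test | Wilcoxon | van Elteren | Adjusted PO | PO − Wilcoxon | van Elteren − Wilcoxon |
|---|---|---|---|---|---|---|---|
| 2.0 | 0 | 54.7 | 55.3 | 54.7 | 55.3 | 0.0 | -0.6 |
| 2.0 | 1 | 51.3 | 51.7 | 52.8 | 53.9 | +2.2 | +1.1 |
| 2.0 | 2 | 43.7 | 44.3 | 50.3 | 51.4 | +7.1 | +6.0 |
| 2.0 | 3 | 34.7 | 35.1 | 47.6 | 48.5 | +13.4 | +12.5 |
| 2.5 | 0 | 75.0 | 76.8 | 75.6 | 76.1 | -0.7 | -1.2 |
| 2.5 | 1 | 72.6 | 73.9 | 74.5 | 75.4 | +1.5 | +0.6 |
| 2.5 | 2 | 64.1 | 65.6 | 73.8 | 74.7 | +9.1 | +8.2 |
| 2.5 | 3 | 52.9 | 54.2 | 69.3 | 70.0 | +15.8 | +15.1 |

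A separate simulation (3,000 trials per setting, OR 2.5) of the stratified rank test against plain Wilcoxon gave 71% versus 65% at d = 2 and 69% versus 53% at d = 3, with about equal power when baseline was uninformative.

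**More uniform entry** (5/10/85%, OR 2.5). The adjusted PO gain over Wilcoxon shrinks to 76.0 − 75.5 = +0.5 at d = 1, 74.9 − 71.1 = +3.8 at d = 2, and 73.9 − 65.9 = +8.0 at d = 3.

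**Type I error.** Adjusted PO 5.0% (d = 2) and 5.7% (d = 3); van Elteren 4.7% and 5.3%.

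**When the effect is not proportional** (Wilcoxon / van Elteren / adjusted PO, %):
- More deaths and more discharges on treatment: 33.5 / 33.0 / 31.0 at d = 0; 26.2 / 25.8 / 24.6 at d = 2.
- More discharges, deaths unchanged: 44.4 / 43.8 / 42.6 at d = 0; 33.8 / 35.0 / 34.0 at d = 2.
- Effect on death and ventilation only: 10.8 / 10.8 / 12.2 at d = 0; 10.8 / 13.4 / 15.2 at d = 2.

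**Chance imbalance.** If 20% are ventilated at entry (an assumption) and allocation is unstratified, the SD of the between-arm difference is √[0.20 × 0.80 × (1/92 + 1/46)] = 0.072. A gap of 10 points or more has z = 0.10/0.072 ≈ 1.38, or about a 17% chance.

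**The case against.** The strongest reply is that nothing here is an error. Under randomisation an unadjusted two-group test is valid. The endpoint is one of several secondary ones with no stated power, and the primary endpoint already measures improvement from baseline. That stands, and it limits the point to efficiency.

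The prognostic strength is also unknown. Scale level 4 pools everyone on supplemental oxygen short of non-invasive ventilation or high-flow cannula, so 2 L patients and non-rebreather patients can share a level. Section 5.2 excludes multi-organ failure requiring vasopressors, CVVH or ECMO, which trims the sickest end. Both could weaken baseline as a predictor. This also stands, and is why the gain must be a range that includes zero.

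A reader might infer that adjustment costs nothing. It does not follow. The proportional-odds model adds an assumption, on a scale that includes death. It lost 2.5 and 1.6 points to Wilcoxon where treatment raised both deaths and discharges. It also estimates something different: at OR 2.5 and d = 2 the mean log odds ratio was 0.94 adjusted against 0.81 unadjusted, whereas sections 2 and 11.2.7 speak of comparing raw scores.

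A reader might also infer that the normality switch costs power. Under proportional odds the t-test and Wilcoxon differ by only 0.4 to 1.8 points. The t-test can fall well behind when the effect is not proportional (30.4% against 44.4% with more discharges, deaths unchanged, d = 0). But a score with 42% of patients at the top level, as assumed here, is unlikely to pass a normality check, so the plan's own Wilcoxon fallback would normally apply. Removing the switch is tidier and is not the main gain.

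**Conclusion.** The point holds as a matter of efficiency. The planned day-14 comparison ignores a recorded baseline score in a population with mixed severity at entry. Using that score changes power by about -1 to +16 points over Wilcoxon at odds ratios of 2.0 to 2.5. It is worth about 0 to 2 points if baseline is weakly prognostic and about 6 to 16 if it is strongly prognostic with the 20/30/50% mix; a more uniform mix roughly halves the upper end. Every one of these figures rests on assumed baseline mixes, prognostic strengths and effect sizes.

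A single strongly prognostic scenario can make the loss look like a fixed 12 to 14 points: with a 20/25/55% mix and a gap of 2.4, 400 replicates gave 40% versus 54% at OR 2.0 and 63% versus 75% at OR 2.5. The documents do not support presenting that as the loss in this trial, and each of those power figures carries a standard error of about 2.5 points. Nor do they support saying that the planned test is invalid or that the 41 events and 80% power are affected.

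**What to change.** Replace the day-14 sentence in section 13.2 with one baseline-adjusted analysis, chosen before outcomes are compared by arm, and drop the normality switch. Either of these would do:

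- A proportional-odds model of the day-14 score on arm and baseline score, reporting the common odds ratio with 95% CI and a stated check of proportionality.
- A Wilcoxon test stratified by baseline score (van Elteren). This avoids the proportional-odds assumption, stays closer to the raw-score objective and kept most of the gain (73.8% against 74.7% for the model and 65.6% for plain Wilcoxon at OR 2.5, d = 2).

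Keep the unadjusted Wilcoxon as a sensitivity analysis. Say how a sparse baseline level will be pooled, since a level holding 5% of 138 patients has about 7. Align section 11.2.7 with the chosen summary measure.

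The cost is wording in sections 13.2 and 11.2.7, with no new data, visits or patients. If the model is chosen, the plan also takes on the proportional-odds assumption, a conditional odds ratio as its estimate, and a possible loss of about 2 points if the effect is not proportional.
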